| DLQI | dermatology life quality index |
| DOB | date of birth |
| eCRF | electronic case report form |
| GCP | Good Clinical Practice |
| GGT | gamma-glutamyl transferase |
| HDL | high-density lipoprotein |
| HED | human equivalent dose |
| hs-CRP | high-sensitivity C-reactive protein |
| ICF | informed consent form |
| ICH | International Conference on Harmonisation |
| IGA | Investigator global assessment |
| IgG1 | immunoglobulin G1 |
| IGRA | Interferon-Gamma Release Assays |

| | |
|------------------|----------------------------------------------|
| IL | interleukin |
| IRB | Institutional Review Board |
| IRT | Interactive Response Technology |
| ISRC | Internal Safety Review Committee |
| IV | intravenous |
| LDL | low-density lipoprotein |
| LDLR | low-density lipoprotein receptor |
| LOX-1 | lectin-like oxLDL receptor-1 |
| Lp(a) | lipoprotein(a) |
| Lp-PLA2 | lipoprotein-associated phospholipase A2 |
| MACE | major adverse cardiovascular events |
| MCP-1 | monocyte chemoattractant protein-1 |
| MDA | malondialdehyde |
| MedDRA | medical dictionary for regulatory activities |
| mg | milligram |
| NOAEL | no-observable-adverse-effect-level |
| oxLDL | oxidized low-density lipoprotein |
| oxHDL | oxidized high-density lipoprotein |
| oxLp(a) | oxidized lipoprotein(a) |
| PASI | psoriasis area and severity index |
| PD | pharmacodynamic |
| PK | pharmacokinetic |
| PT | prothrombin time |
| SAA | serum amyloid A |
| SAE | serious adverse event |
| SC | subcutaneous |
| SOP | standard operating procedure |
| TEAE | treatment-emergent adverse event |
| TK | toxicokinetic |
| T _{max} | time of maximum concentration |
| TNF α | tumor necrosis factor-alpha |
| TPV | total plaque volume |
| TST | tuberculin skin test |
| VLDL | very low-density lipoprotein |

WHO

World Health Organization

1 INTRODUCTION AND RATIONALE FOR DOSE SELECTION

1.1 Background Information

Orticumab is a fully human, recombinant monoclonal immunoglobulin G1 (IgG1) antibody that targets oxidized low-density lipoprotein (oxLDL) through binding to a specific epitope expressed in apolipoprotein B-100 (ApoB-100), the protein portion of LDL. It preferentially binds oxLDL over native LDL and reduces oxLDL-mediated inflammation¹. Orticumab is being developed for the treatment of subjects with plaque psoriasis.

OxLDL is significantly increased in subjects with psoriasis and is found in lesional, but not in non-lesional skin of psoriatic subjects, and plasma levels of oxLDL correlate with the psoriasis area and severity index (PASI).²⁻⁶ The main receptor for oxLDL (lectin-like oxLDL receptor-1 [LOX-1]) has been shown to be expressed in the epidermis.⁷⁻¹⁰ The presence of LOX-1 perpetuates oxLDL-mediated inflammation in the skin, and because oxLDL also promotes LOX-1 upregulation, a feed-forward loop is created that stimulates chronic inflammation.¹¹ OxLDL promotes inflammation via endothelial dysfunction^{12,13} and macrophage activation and the subsequent release of proinflammatory cytokines, including those identified as pathogenic mediators of psoriasis.^{3,4} An in vitro assessment of TNF α -stimulated keratinocytes found that oxLDL was responsible for driving IL-23 expression, demonstrating that oxLDL upregulates a known pathogenic mediator of psoriasis, and the target of current standard of care therapeutics.¹¹ These data further suggest that targeting oxLDL may be an effective approach for treating psoriasis.

Non-clinical safety pharmacology and toxicology studies have been performed with orticumab in support of early clinical trials. During the conduct of these nonclinical studies, no toxicological findings were identified that could be related to drug treatment at exposures up to several orders of magnitude higher than those that appear to produce pharmacological effects in in vitro and in vivo animal models of cardiovascular disease.

Orticumab has been tested in humans in 3 clinical studies: two Phase 1 studies and one Phase 2 study. In the first-in-human Phase 1 study, orticumab was administered to 28 healthy volunteers as a single intravenous (IV) infusion at doses of 0.007 to 15 mg/kg or as a single SC injection at 1.25 mg/kg (n=6); in the multiple dose phase of this study, orticumab was administered weekly for 4 weeks via IV infusion at doses of 0.25 to 15 mg/kg or via SC injection at 1.25 mg/kg (n=6).

In the second (bioavailability) Phase 1 study, orticumab was administered as a single dose of 360 mg via IV or subcutaneous (SC) injection to (n=22) healthy volunteers. In both studies, orticumab demonstrated linear pharmacokinetics with a half-life of 2-3 weeks. Orticumab was safe and well tolerated in both studies without any reports of treatment-related serious adverse events (SAEs). Local injection site reactions were observed but were mild in intensity and resolved within a few days to slightly more than 1 week without medical intervention.

In the Phase 2 study, (n=49) subjects with stable atherosclerotic cardiovascular disease were administered orticumab via IV [REDACTED] as a single dose followed by [REDACTED]

████████ weekly for 3 weeks then monthly for 2 months. No SAEs due to study drug were reported. All adverse events (AEs) were mild or moderate in severity, with the most common AEs being dizziness, headache, and gastrointestinal (mainly diarrhea). No anti-therapeutic antibodies (ATAs) to orlicumab were observed during or after treatment. No dose-limiting toxicities, deaths, or pregnancies were reported.

1.2 Rationale for Study and Dose Selection

OxLDL is an established driver of CVD and atherosclerotic plaque development.^{14,15} OxLDL is also a potential target for the treatment of psoriasis. OxLDL promotes inflammation via macrophage activation and the subsequent release of proinflammatory cytokines, including those identified as pathogenic mediators of psoriasis,^{3,4} and promotes endothelial dysfunction,¹² an important process implicated in the pathogenesis of psoriasis.¹³ OxLDL is significantly increased in subjects with psoriasis and is found specifically in psoriatic skin lesions, but not unaffected skin from the same subject.³⁻⁶ Furthermore, plasma levels of oxLDL correlate with the PASI score used to measure psoriatic disease activity.²

The dual role oxLDL plays in contributing to both psoriasis disease pathogenesis and its primary comorbidity (CVD), make oxLDL a promising target for the potential treatment of subjects with psoriasis.

In the Phase 2 study listed above (NCT01258907), 2 subjects with psoriasis reported improvements in psoriatic plaque lesions. Anecdotal information provided from the subjects to the Investigators were: 1) improvement after one dose of orlicumab in one subject and 2) improvement in elbow and knee plaque psoriasis despite being refractory to both phototherapy and steroids in the second subject. Neither subject was receiving treatment for psoriasis during this study. While anecdotal and in only 2 subjects, this information along with the role of oxLDL in psoriasis suggest a study of orlicumab in subjects with psoriatic disease is warranted.

Given that no information is known regarding optimized dosing regimen or route of administration, it is decided that IV administration of the maximal allowable dose of orlicumab should be chosen to maximize the potential to observe a clinically relevant efficacy signal.

Orlicumab administered IV or SC is well tolerated by cynomolgus monkeys after repeat dosing, including weekly SC doses of up to 150 mg/kg for 26 weeks. The NOAEL for orlicumab derived from the pivotal repeat dose toxicology studies in cynomolgus monkeys was determined to be ██████████ after 4 or 26 weeks of administration. The HED of the monkey NOAEL is 4926 mg (or 59.4 mg/kg), based on a mean body weight of 83 kg obtained from the Phase 2 study of orlicumab in subjects with stable atherosclerosis.

In the Phase 1 first-in-human study, a dose of 15 mg/kg IV weekly for 4 weeks was well tolerated by healthy volunteer subjects with elevated circulating oxLDL. Following multiple IV dose administration of orlicumab in the Phase 2 proof of activity study in subjects with stable atherosclerosis (NCT01258907); ██████████ on Day 1 and ██████████ on Days 8, 15, 22, 50, and 78), the C_{max} was 286 and 197 ug/mL (resulting in ~19-fold safety margin based on C_{max}) after the first and last dose, respectively. Mean trough serum concentrations on Days 22, 78, and 169 (12 weeks after the last dose administration) were 63.1, 15.4, and 2.47 ug/mL, respectively. No dose limiting SAEs were observed and orlicumab was well-tolerated at this high dose by the patients.

The dosing regimen in the first month of this Phase 2 psoriasis proof-of-activity study involves fixed weekly doses of [REDACTED] IV. This approximates to [REDACTED] once weekly for a subject of relatively short stature and a BMI of 30 (the minimum BMI for eligibility for enrolment), with subjects of taller stature and higher BMI receiving lower doses on a mg/kg basis. Hence, the dosing regimen in the Phase 2 psoriasis proof-of-activity study can be supported by the favorable safety profile of the 15 mg/kg once weekly dose in healthy subjects in the first-in-human study. In addition, the atherosclerosis study (NCT01258907) provides relevant data on safety of more prolonged exposure (albeit at lower doses than proposed for the Phase 2 psoriasis proof-of-activity study). The NOAELs in the 4-week IV monkey study (Study2090-007) and 26-week SC monkey study (Study07-1492) of [REDACTED] q1w (the highest doses evaluated) correspond to a human equivalent dose (HED) of 48mg/kg q1w (for a 60kg human based on normalization to body surface area), which is approximately 3-fold higher than proposed for use during the first month of the Phase 2 proof of activity study.

Because the temporal relationship between orticumab PK and PD in humans is not known, our dosing regimen is designed to administer the maximal allowable concentration of orticumab to the subjects in the first 4 weeks of treatment. Given that the mean elimination half-life of orticumab at this dose is approximately 2-3 weeks, a weekly dosing regimen is consistent with the therapeutic goal of ensuring pharmacologically relevant blood concentrations of orticumab over the initial 4-week period. Because the link between PK and PD has not been established, blood samples are taken just prior to dosing (minimum concentration [C_{min}]) on day 8, 15, 22, 29, 58 and 87 to confirm trough levels of orticumab to ascertain intersubject differences concentrations associated with potential differences in PD measures.

In summary, the results of the in vivo safety studies support the proposed clinical program and provide adequate safety factors to support x 4 weekly, followed by x 2 monthly administration of [REDACTED] orticumab in the planned Phase 2 study in psoriasis.

1.3 Rationale for Subject Population

Psoriasis is a risk factor for cardiovascular disease (CVD), and CVD is the primary cause of morbidity and mortality in subjects with psoriasis.^{13,16,17} Subjects with psoriasis have a 25% increase in relative risk for CVD,^{16,18} and those with severe psoriasis were found to have a 6.2% increase in the 10-year absolute risk of MACE compared with the general population.^{16,17} The association between psoriasis and CVD is further demonstrated by the fact that improvement in psoriasis disease activity results in improvement in aortic vascular inflammation.¹⁹

OxLDL is significantly increased in subjects with psoriasis and is found specifically in psoriatic skin lesions, but not unaffected skin from the same subject.³⁻⁶ The dual role oxLDL plays in contributing to both psoriasis disease pathogenesis and its primary comorbidity (CVD), make oxLDL a promising target for the potential treatment of subjects with psoriasis.

While mild-to-moderate psoriasis is typically controlled with topical creams and phototherapy, moderate-to-severe psoriasis requires oral, systemic anti-inflammatory medications (i.e., methotrexate) and/or injectable biologics. Although these therapies are effective at managing symptoms and improving healing in subjects with psoriasis, they are associated with significant side effects due to their broad, systemic immune-suppressing activity. Therefore, reducing disease activity while preventing off-target effects remains an unmet need in this subject

population. The moderate-to-severe psoriatic subjects with CVD comorbidities are therefore the most relevant target population to investigate the effects of orticumab on both local and systemic chronic inflammation.

2 STUDY OBJECTIVES AND ENDPOINTS

| Objectives | Endpoints |
|---------------------------------------------------------------------------------------------------------------------------------------------------------------------------------------------------------------------------------------------------------------------------------------------------------------------------------------------------------------------------------------------------------------------------------------------------------------------------------------------------------------------------------------------------------------------------------------------------|-----------------------------------------------------------------------------------------------------------------------------------------------------------------------------------------------------------------------------------------------------------------------------------------------------------------------------------------------------------------------------------------------------------------------------------------------------------------------------------------------------------------------------------------------------------------------------------------------------------------------------------------------------------------------------------------------------------------------------------------------------------------------------------------------------------------------------------------------------------------------------------------|
| Primary Safety Objective: | Primary Safety Endpoints: |
| 1. To assess the safety and tolerability of orticumab [REDACTED] in subjects with moderate-to-severe psoriasis and cardiometabolic risk factors, as assessed by vital signs, clinical laboratory variables, and adverse events (AEs) monitoring, compared to placebo. | 
 1. Number and percent of participants with one or more Treatment Emergent Adverse Events (TEAEs) or any serious adverse events (SAEs). 2. Change in hemodynamic parameters from Baseline to Weeks 3, 7, 11 and 15. 3. Change in blood chemistry and hematology from Baseline to Weeks 3 and 15. 4. Change in physical examination from Baseline to Weeks 3, 7, 11 and 15. |
| Primary Efficacy Objective: | Primary Efficacy Endpoints: |
| 1. To demonstrate the efficacy of orticumab [REDACTED] in subjects with moderate-to-severe psoriasis and cardiometabolic risk factors with respect to both percent change in PASI and sIGA mod 2011 response at Week 15, compared to placebo. | 
 1. Mean percent change from Baseline in PASI at Week 15, compared to placebo. 2. Percentage of participants achieving treatment success (clear =0 or almost clear =1) and greater than or equal to (\geq) 2 Point Improvement at Week 15 on the 5-point static Investigator's Global Assessment modified 2011 version (sIGA). |
| Secondary Efficacy Objectives: | Secondary Efficacy Endpoints: |
| 
 1. To demonstrate the efficacy of orticumab [REDACTED] in subjects with moderate-to-severe psoriasis and cardiometabolic risk factors with respect to percent change in PASI and PASI response by looking at PASI 75 and 50 response rates and sIGA mod 2011 response at Weeks 1, 3, 7, and 11, compared to placebo. 2. Assess the effect of orticumab [REDACTED] on BSA, Dermatology Life Quality Index (DLQI), and Itch Numerical Rating Scale Score in subjects with moderate-to-severe psoriasis and cardiometabolic risk factors. | 
 1. Mean percent change from Baseline in PASI at Weeks 1, 3, 7 and 11. 2. Percentage of Participants achieving PASI75 and PASI50 from Baseline at Weeks 1, 3, 7, and 11, compared to placebo. 3. Percentage of participants achieving treatment success (clear =0 or almost clear =1) and greater than or equal to (\geq) 2 Point Improvement at Weeks 1, 3, 7, and 11 on the 5-point static Investigator's Global Assessment modified 2011 version (sIGA). 4. Mean percent change from Baseline in BSA at Weeks 1, 3, 7, 11, and 15, compared to placebo. 5. Mean change from Baseline in Dermatology Life Quality Index (DLQI) at Weeks 3, 7, 11, and 15, compared to placebo. 6. Mean change from Baseline in Itch Numerical Rating Scale Score at Weeks 3 and 15, |

| | |
|-----------------------------------------------------------------------------------------------------------------------------------------------------------------------------------------------|------------------------------------------------------------------------------------------------------------------------------------------------------------------------------------------------------------------------------------------------------------------------------------------------------------------------------------------------------------------------------------------------------------------------------------------------------------------------------------------------------------------------------------------------------------------------------------------------------------------------------------------------------------------------------------------------------------------------------------------------------------------------------------------------------------------------------------------------------------------------------------------------------------------------------------------------------------------------------------------------------------------------------------------------------------------------------------------------------------------------------------------------------------------------------------------------------------------------------------------------------------------------------------------------------|
| | compared to placebo. |
| Exploratory Objective: | Exploratory Efficacy Endpoints: |
| 
1. Assess the effect of orticumab [REDACTED] [REDACTED] on cardiometabolic and inflammatory biomarkers in subjects with moderate-to-severe psoriasis and cardiometabolic risk factors.
 | 
1. Mean change from Baseline in cardiometabolic and inflammatory biomarkers at Weeks 3 and 15 in:
 
 ○ Blood serum lipid parameters 
 ▪ ApoB, Apo A1, VLDL-c, oxLDL, oxHDL, Lp(a), oxLp(a), NMR-LP4 ○ Blood serum inflammation biomarkers 
 ▪ Interleukin-6 (IL-6), IL-1β, IL-17, tumor necrosis factor-alpha (TNF-α), osteoprotegerin, high-sensitivity C-reactive protein (hs-CRP), serum amyloid A (SAA), and monocyte chemoattractant protein-1 (MCP-1) ○ Blood serum HDL efflux efficiency 
 ▪ ABCA-1 
2. Change in coronary artery perivascular fat attenuation index (FAI) measured by coronary computed tomographic angiography (CCTA) at Week 15 as compared to Baseline in active and placebo treated subjects.
 
3. Change in Noncalcified and low attenuation coronary artery plaque volume, assessed by CCTA at week 15 as compared to Baseline, in active and placebo subjects.
 
4. Change in total plaque volume, assessed by CCTA at week 15 as compared to Baseline, in active and placebo subjects.
 |

3 INVESTIGATIONAL PLAN

3.1 Overall Study Design and Plan: Description

This randomized, double-blind study is designed to compare the responses of orticumab [REDACTED] or placebo in subjects with moderate to severe psoriasis. A total of 75 subjects (enrolled in at least 17 study sites) with psoriasis will be randomized in a double-blind fashion to receive either an IV infusion of orticumab or placebo for up to 78 days. Before any study-related procedures are conducted, the subjects will sign a written informed consent. Subjects will be screened (Day -28 to -1) for the study, which will include clinical laboratory evaluations and CCTA. Prior to dosing on study Day 1, Baseline assessments will be performed. During treatment periods, dosing will be performed under supervision at the research center. Subjects will visit the research center on the morning of Days 1, 8, 15, 22, 50, and 78 for a pre-dose blood sample for PK purposes, Day 106 for End of Study assessments, and Day 120 for Follow-up assessments.

Following the Screening Period, participants will be enrolled into one of the two groups: [REDACTED] orticumab or placebo. Subjects will be randomized in a 2:1 ratio, orticumab to placebo and receive up to 11 weeks of treatment.

Planned treatments are weekly for 4 weeks, then monthly IV infusions of [REDACTED] orticumab or placebo. The Internal Safety Review Committee (ISRC) will review the blinded safety data after the first subject completes the first dose (Day 1), the first five subjects complete the first dose (Day 1), and the first ten subjects complete the first dose (Day 1). The IRSC will review all adverse reactions to all administered doses at these times. At the Investigator's discretion, subjects may be eligible for psoriasis rescue medications as discussed in [Section 5.9.4](#).

Stopping criteria ([see Section 12.2](#)) will be utilized in this study based on treatment-emergent AEs (defined as AEs that begin or worsen after the first dose of IP) in determining if infusions in existing and future subjects may continue.

The following efficacy analyses measures will be assessed during the study:

- **Psoriasis Area and Severity Index (PASI)**

The PASI combines assessments of 4 body areas: the head and neck (H), the upper limbs (UL), the trunk (T) and the lower limbs (LL). The percentage of skin affected by psoriasis in each area is given a numerical score representing the Percentage involved: 1(0–9%), 2 (10–29%), 3 (30–49%), 4 (50–69%), 5 (70–89%) or 6 (90–100%). Within each area (H, UL, T, LL) the severity of 3 plaque signs –erythema (E), thickness/induration (I) and desquamation/scaling (D) –is assessed on a 5-point scale: 0 (none), 1 (mild), 2 (moderate), 3 (severe) or 4 (very severe). The assessment of lesion severity and area affected are combined into single score. The final PASI will be = sum of severity parameters for each region*area score*weight of region (where head: 0.1, arms: 0.2, body: 0.3, legs: 0.4); total possible score range: 0=no disease to 72=maximal disease. The maximum PASI score that can be measured will be <72 since the PASI assessment will exclude scalp, palms, fingernails, soles, and toenails.

Video training will be mandatory for trial investigators involved in this assessment.

Reduction in PASI score from Baseline indicates improvement. The percentage change will be calculated by subtracting the weeks 1, 3, 7, 11 and 15 values from the Baseline values. The percentage change will be calculated for each entire treatment group (not for each participant). A positive percentage change from Baseline will indicate improvement (Bozek 2017).

- **Body Surface Area (BSA)**

Scored as the percentage body area affected by psoriasis; 0–100%. A commonly used method to estimate the body surface area of psoriatic lesions is the “rule of nines”, which was originally developed for estimating the surface area of burns. It is defined as 9% coverage for the head and neck, 9% for each arm, 9% for the anterior and posterior legs, and 9% for each of 4 trunk quadrants, leaving 1% for the genitalia. The BSA can also be estimated by the number of a subject’s hand areas affected, on the assumption that one “handprint” reflects approximately 1% of BSA (Bozek 2017, Spuls 2010).

Training will be mandatory for trial investigators involved in this assessment.

- **Investigator Global Assessment (IGA)**

The IGA is a 5-category scale including “0 = clear”, “1 = almost clear”, “2 = mild”, “3 = moderate” or “4 = severe” indicating the physician’s overall assessment of the psoriasis severity focusing on induration, erythema and scaling. Treatment success of “clear” or “almost clear” consists of no signs of psoriasis or normal to pink coloration of lesions, no thickening of the plaque, and none to minimal focal scaling. The IGA captures and categorizes the global assessment of all clinical signs and symptoms of disease. This scale will be scored as a static assessment; i.e., without regard to a previous assessment. To have IGA success, one must have a designation of ‘clear’ or ‘almost clear’ and exhibit a two-point improvement from Baseline. Hence, if a subject has ‘mild’ disease at Baseline, he/she must reach ‘clear’. If a subject has ‘moderate’ disease at Baseline, he/she must reach ‘almost clear’.

And, if a subject is classified as ‘severe’ at Baseline, he/she must still reach ‘almost clear’, even though that requires a three-point improvement.

Training will be mandatory for trial investigators involved in this assessment.

- **Itch Numeric Rating Scale (I-NRS)**

The Itch NRS is a self-administered subject reported outcome questionnaire that is completed during protocol specified clinic visits. Participants indicate itch severity by circling the integer that best describes the worst level of itching due to psoriasis in the past 24 h on an 11-point scale anchored at 0, representing ‘no itching’ and 10, representing ‘worst itch imaginable’.

- **Dermatology Life Quality Index (DLQI)**

DLQI is the dermatology-specific quality of life measure used for psoriatic population. The 10-item questionnaire assesses participant health-related quality of life (daily activities, personal relationships, symptoms and feelings, leisure, work and school, and treatment). The DLQI questions are rated by the participant as 0 (not at all/not relevant) to 3 (very much) with a total score range of 0 (best) to 30 (worst); higher scores indicate poor quality of life. Patient's Global

Assessment (PtGA)-The PtGA asks the participant to evaluate the overall cutaneous disease at that point in time on a single item, 5-point scale (0=clear; 1=almost clear; 2=mild; 3=moderate; 4=severe).

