8.4 Efficacy Analysis

8.4.1 Primary Efficacy Evaluation

There are two primary endpoints for this study: Percent change in PASI and sIGA response rate.

Percent change in PASI will be analyzed using a linear mixed model analysis. The model will be implemented using PROC MIXED in SAS, and will include fixed effects for treatment, site and Baseline PASI as a covariate.

The sIGA response rate will be analyzed using Fisher's Exact Test with treatment and response as the factors.

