1.3.4 Primary Endpoints

The primary safety endpoints for the study are:

1. Number and percent of participants with one or more Treatment Emergent Adverse Events (TEAEs) or any serious adverse events (SAEs).
2. Change in hemodynamic parameters from Baseline to Weeks 3, 7, 11 and 15.
3. Change in blood chemistry and hematology from Baseline to Weeks 3 and 15.
4. Change in physical examination from Baseline to Weeks 3, 7, 11 and 15.

The primary efficacy endpoints for the study are:

1. Mean percent change from Baseline in PASI at Week 15, compared to placebo.
2. Percentage of participants achieving treatment success (clear =0 or almost clear =1) and greater than or equal to (\geq) 2 Point Improvement at Week 15 on the 5-point static Investigator's Global Assessment modified 2011 version (sIGA).

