1.3.5 Secondary Endpoints

The secondary efficacy endpoints for the study are:

1. Mean percent change from Baseline in PASI at Weeks 1, 3, 7 and 11.
2. Percentage of Participants achieving PASI75 and PASI50 from Baseline at Weeks 1, 3, 7, 11 and 15 compared to placebo.
3. Percentage of participants achieving treatment success (clear =0 or almost clear =1) and greater than or equal to (\geq) 2 Point Improvement at Weeks 1, 3, 7, and 11 on the 5-point static Investigator's Global Assessment modified 2011 version (sIGA).
4. Mean percent change from Baseline in BSA at Weeks 1, 3, 7, 11, and 15 compared to placebo.
5. Mean change from Baseline in Dermatology Life Quality Index (DLQI) at Weeks 3, 7, 11, and 15 compared to placebo.

6. Mean change from Baseline in Itch Numerical Rating Scale Score at Weeks 3 and 15 compared to placebo.

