2.9.3. Psoriasis Area and Severity Index (PASI)

PASI total score, change from baseline and percent change from baseline will be calculated for each post-baseline visit. The difference between active and placebo will be tested using a mixed effects linear model (PROC MIXED in SAS) that will include fixed effects for treatment and site with Baseline PASI total score as a covariate at each post-baseline visit.

PASI75 (75% improvement from baseline in PASI total score) and PASI50 (50% improvement from baseline in PASI total score) responder rates will be derived and analyzed using a Fisher's exact test to test for differences between placebo and active at Weeks 1, 3, 7, 11 and 15.

2.9.4. static Investigator Global Assessment (sIGA)

The sIGA will be summarized at each visit using frequency counts. The difference between active and placebo will be tested using a Cochran-Mantel-Haenszel (CMH) test at each visit that sIGA is collected.

Treatment success in sIGA is defined as having a value of clear=0 or almost clear=1 and greater than or equal to a 2 point improvement on the 5-point static Investigator's Global Assessment test. Responder rates based on treatment success will be summarized and analyzed using a Fisher's Exact test at each post-baseline visit that sIGA is collected.

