2.9.8. Itch Numeric Rating Scale (I-NRS)

The I-NRS will be summarized at each visit using frequency counts. The difference between active and placebo will be tested using a Cochran-Mantel-Haenszel (CMH) test at each visit that I-NRS is collected.

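### Protocol 3.1 defines PASI percent change per treatment group, which conflicts with the primary endpoint and its model; separately, SAP 2.9.8 does not estimate the itch change named as an endpoint

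*Protocol*

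**What the plan says.** **PASI.** The first primary efficacy endpoint in SAP 1.3.4 is "Mean percent change from Baseline in PASI at Week 15, compared to placebo", and Protocol section 2 says the same. Protocol 3.1, where the PASI is described, gives three rules:

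- On arithmetic: "The percentage change will be calculated by subtracting the weeks 1, 3, 7, 11 and 15 values from the Baseline values". No division by baseline is written.
- On level: "The percentage change will be calculated for each entire treatment group (not for each participant".
- On sign: "A positive percentage change from Baseline will indicate improvement".

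Protocol 8.4.1 analyses percent change in PASI with a linear mixed model: "The model will be implemented using PROC MIXED in SAS, and will include fixed effects for treatment, site and Baseline PASI as a covariate". SAP 2.9.1 repeats this. SAP 2.9.3 says "PASI total score, change from baseline and percent change from baseline will be calculated for each post-baseline visit", applies the model at each post-baseline visit, and derives PASI50 and PASI75 responders. The SAP does not repeat the group-level rule, and it gives no formula or sign for percent change.

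**Itch.** The secondary endpoint in SAP 1.3.5 is "Mean change from Baseline in Itch Numerical Rating Scale Score at Weeks 3 and 15 compared to placebo"; Protocol section 2 and Protocol 6.5.1 agree. SAP 2.9.8 says "The I-NRS will be summarized at each visit using frequency counts" and adds a CMH test between arms at each visit where the scale is collected. It mentions no change score, mean or baseline covariate. Protocol Table 1 collects the itch scale at Visit 1, Week 3 and Week 15.

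**The concern.** A percent change computed once per arm is not a mean of percent changes. It has no between-participant variance, it cannot be the response in a model with baseline PASI as covariate, and it yields no responder status. The Protocol rule and the planned analysis therefore cannot both be followed. The endpoint affected is the first in the testing hierarchy: Protocol 8.8 and SAP 2.10 allow sIGA to be tested only if percent change in PASI succeeds, at the interim and at the final analysis. Its definition should be unambiguous.

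The itch point is separate and lesser. The section meant to deliver a mean change from baseline does not specify one, and it leaves unused a baseline value the trial collects.

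**Working it through.** **1. PASI: what each part of the plan needs**

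| Place | Unit required |
|---|---|
| Protocol 3.1, calculation rule | One value per arm |
| Protocol 2 and SAP 1.3.4, mean percent change | One value per participant, then averaged |
| Protocol 8.4.1 and SAP 2.9.1, mixed model with baseline covariate | One value per participant |
| SAP 2.9.3, PASI50 and PASI75 | One value per participant |
| SAP 2.11, power from an SD of percent change | One value per participant |

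**2. The SAP's power figures rest on participant-level values.** Inputs from SAP 2.11: SD 10 points; 80% power for a 7-point difference and 90% for 8 points. From SAP 2.10 and 1.2: 75 subjects at 2:1, so 50 and 25. SAP 2.11 states no alpha; two-sided 0.05 is assumed.

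- SE = 10 × √(1/50 + 1/25) = 2.449
- 7 points: Φ(7/2.449 − 1.960) = Φ(0.898) = 81.5%
- 8 points: Φ(8/2.449 − 1.960) = Φ(1.306) = 90.4%

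Both agree with the stated figures within 2 points. (At the final-analysis alpha of 0.04 they are 78.9% and 88.7%; the present point does not depend on the choice.) The SD of 10 is a spread between participants and does not exist under the group rule.

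**3. How far apart the two quantities can be.** Let B be baseline and P the participant's percent improvement. Taking the group figure as the percent change in the arm's mean PASI:

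group figure = ΣBP / ΣB = mean(P) + Cov(B, P) / mean(B)

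So it is an average weighted by baseline, and it equals the mean percent change only when improvement is uncorrelated with baseline.

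- Constructed extreme, two subjects: 12 to 3 (75%) and 40 to 30 (25%). The mean is 50.0%; the group figure is (52 − 33)/52 = 36.5%.
- Opposite direction: 12 to 11 (8.3%) and 40 to 10 (75%). The mean is 41.7%; the group figure is (52 − 21)/52 = 59.6%.
- Milder case, all inputs assumed: baseline mean 20, SD 5.64, mean improvement 30%, improvement changing by −1 to +1 point per PASI unit. The gap is ±1 × 5.64²/20 = ±1.6, so the group figure runs from 28.4% to 31.6%.

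**4. Itch: comparison with the sister endpoints.** SAP 2.9.5 (BSA) and 2.9.6 (DLQI) derive change from baseline and model it with treatment, site and the baseline value. SAP 2.9.2 sends continuous secondary variables to a mixed model. SAP 2.9.8 does neither for itch.

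**5. Itch: precision.** Let ρ be the correlation between baseline and follow-up, which the documents do not give. Relative to a baseline-adjusted analysis, the raw follow-up score has variance ratio 1/(1 − ρ²). Relative to the raw score, an unadjusted change score has variance 2(1 − ρ), assuming equal SDs. The power columns also assume SD 2.5, a true difference of 1.5, 40 and 20 completers, and two-sided alpha 0.05.

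| ρ (assumed) | Raw / adjusted variance | Change / raw variance | Power: raw | Power: change score | Power: adjusted |
|---|---|---|---|---|---|
| 0.3 | 1.10 | 1.40 | 59% | 46% | 63% |
| 0.5 | 1.33 | 1.00 | 59% | 59% | 72% |
| 0.7 | 1.96 | 0.60 | 59% | 81% | 87% |

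These figures ignore the degrees of freedom used by site effects.

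**The case against.** **On PASI.** The analysis sections do produce the stated endpoint. The model, the responder rates and the planned listing of PASI derived parameters for all subjects (SAP 4.1 and 4.2) make sense only at participant level, and Protocol section 8 leaves further detail to the SAP. Nobody could run the specified model from the group-level sentence, which suggests a drafting slip. The missing sign in the SAP is minor, since reversing it leaves a two-sided p-value unchanged. All of this stands. A reader might infer that the plan computes only a group figure and that the primary analysis is untestable; the documents do not support that. What remains is that the sentence is in force, its bracketed words exclude a looser reading, and the SAP neither says per participant nor acknowledges departing from it.

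**On itch.** CMH is defensible for an 11-point integer scale. If SAP 2.9.8 means the row mean score version named in SAP 2.9.2, it compares mean scores between arms. Under randomisation, the expected difference in follow-up means equals the expected difference in mean change, so a relevant test does exist. SAP 2.1 allows descriptive statistics for derived variables where appropriate, and the table shells are in a separate file, so it would be too firm to say that the change will never appear anywhere. Nor should the precision figures be read as the cost of omitting a change score: at ρ = 0.5 an unadjusted change score gains nothing over the raw score, and at 0.3 it is worse. The gain comes from baseline adjustment and depends on an assumed correlation. What remains is that the section written for this endpoint specifies neither the change nor any use of baseline.

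**Conclusion.** Both points hold, as inconsistencies to be corrected.

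For PASI, Protocol 3.1 contradicts the endpoint, the model, the responder analyses and the basis of the power statement. The primary result is at risk only if the Protocol sentence is followed in place of the analysis sections. Even then the size depends on how improvement varies with baseline: about 1.6 points in the milder assumed case, with the two-subject examples serving only to show that the quantities differ.

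For itch, SAP 2.9.8 as written does not estimate the stated endpoint and does not use the collected baseline. Ignoring small-sample and site-effect costs, baseline adjustment is expected to be at least as precise as raw scores, with variance ratios of 1.10 to 1.96 over assumed correlations of 0.3 to 0.7. This is a secondary endpoint outside the PASI-then-sIGA hierarchy and should not borrow weight from the primary-endpoint conflict.

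**What to change.** - **Protocol 3.1.** Replace the group-level sentence and the subtraction rule with: percent change is calculated for each participant as 100 × (Baseline − visit)/Baseline, positive meaning improvement, and is then averaged by arm. The division is safe because eligibility requires a PASI of at least 12.
- **SAP 2.9.3.** State the same formula and sign. If the SAP is corrected before the Protocol can be amended, say explicitly that this definition replaces the one in Protocol 3.1.
- **SAP 2.9.8.** Analyse I-NRS change from baseline at Weeks 3 and 15 with the model used for DLQI: treatment and site as fixed effects, baseline I-NRS as covariate. Report the adjusted mean difference with its confidence interval. Keep the frequency counts and CMH test as supportive, and name the CMH version.

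The cost is a short replacement in the Protocol, a line in SAP 2.9.3 and a paragraph in SAP 2.9.8. The DLQI model code is reused; no data collection, sample size or design feature changes. Protocol section 10 requires IRB approval for the Protocol wording, so it can go with the next amendment.
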